- Our primary objective is to assess the efficacy of a long- acting antihistamine, Cetirizine, on opioid- induced pruritus in a double-blind, placebo controlled study. The primary outcome will be number of treatment failures between the treatment and placebo groups. Treatment failure is defined as persistent itch score of > 3 3hrs after receiving the intervention.
- 2. Our secondary objectives are to analyze:
 - The correlation between baseline serum tryptase levels and the occurrence of opioid- induced pruritus.
 - The effect of age, race, sex on opioid induced pruritus and the influence of these parameters on antipruritic effect of the drug.

Methods:

Subject recruitment:

This study is a randomized, double blind placebo controlled study. Subjects 6-18yrs of age, requiring treatment with oral or intravenous opioids will be recruited from the pediatric inpatient units at Children's Hospital of Richmond at VCU.

Inclusion criteria:

- Children age 6-18yrs on opioids who develop pruritus and are willing to participate in the study

Exclusion criterias:

- Children with history of chronic urticaria
- Children with other chronic pruritic condition like eczema, contact dermatitis, psoriasis
- Children with known hypersensitivity to cetirizine/zyrtec
- Children on second generation antihistamine 1 week prior to the study recruitment
- Children who are unwilling or unable to swallow the capsule.
- Children with chronic liver or kidney disease

Study Design:

After obtaining an informed consent from the parent or guardian, and an informed assent from children ages 12 years and above, serum tryptase levels will be drawn at baseline. For subjects whose baseline tryptase could not be drawn prior to the onset of itch symptom, a second attempt will be made either 24hrs after being symptom free or at a later date either in the inpatient or outpatient setting when they are free of symptoms.

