Subjects who develop pruritus will have a baseline itch score measured at the onset of the itch symptom. Subjects with itch score of ≥ 3 will be randomized in a double blind fashion to the treatment group with cetirizine 10 mg once daily or to the placebo group. A tryptase level will be obtained 15-60 minutes after the onset of itching. Subjects will have itch scores measured at two time points from receiving the intervention, one at 3hours and other at 12 hours. Subjects will be allowed to receive rescue Diphenhydramine (Benadryl) 3 hours post intervention at the discretion of the treating physician.

Treatment failure is defined as an itch score of ≥3 at 3 hours post intervention and will result in discontinuation from the study. Successfully treated subjects will have a second itch score measured at 12 hours post intervention to analyze the persistence of antipruritic effect of the intervention. The numbers of treatment failures in each group are recorded. The total number of rescue Benadryl doses in each group will also be

recorded. The opioid dose, interval and total doses that each subject receives will be recorded. Patients whose treatment has been successful in controlling the pruritus (itch score ≤ 2) will continue in that arm for a maximum of 12 hours or till discharge whichever is earlier. Patients may drop out of the study at any time. The reason for dropping out will be recorded. At the conclusion of the study, patients will be reassessed by the primary team for further need for any anti-pruritic medications.

Primary Outcome

Number of treatment failures in the study group versus the placebo group at 3 hours post randomization

Secondary Outcomes:

- 1. Number of drop outs in the study group versus the placebo group at the end of the study period.
- 2. Tryptase levels (Total and mature) in subjects who develop opioid-induced pruritus versus those who do not.
- 3. Change in Tryptase levels (Total and mature) from baseline in subjects who develop pruritus
- 4. Effect of age, race, and sex on the incidence of opioid-induced pruritus
- 5. Effect of age, race, and sex on response to cetirizine in subjects with opioid-induced pruritus.
- 6. Change in the baseline itch score between treatment and the placebo group.
- 7. Number of rescue Benadryl doses between treatment and the placebo group.

Preliminary Results:

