Based on our experience (n=16) over the last few months, 37% (n=6) of patients treated with opioids in the inpatient setting develop pruritus. Of those 6 patients, 66.6% were successfully treated with an antihistamine and were able to continue treatment on the same opioid.

Statistical Method:

Data will be analyzed using Chi square, student t-tests and Mann-Whitney U test (for non-parametric data) where appropriate. A p value of <0.05 will be considered significant.

Assuming a 50% reduction in the failure rate to be clinically significant, a sample size of 66 confers a power of 0.8 at α =0.05. Assuming a 10% drop out rate in each group a total of 73 patients will be recruited.

Time line:

We plan to recruit at least 1 patient per week for this study. The study should be completed in 2years. There is a real chance of completing this study much earlier than the 2 year time frame.

Investigator responsibilities:

- The study will be approved by the Western Institutional Review Board
- Conduct the study smoothly and effectively
- Report any adverse effects to McNeil Pharmaceuticals.
- At the completion of the study the data will be presented to McNeil before sending in for publication.

Future research direction:

- 1. To analyze the effect of antihistamine on opioid-induced itching in a much larger sample size.
- 2. To investigate titration prick skin testing to opioid as a predictor of opioid-induced itching.

Limitation of the study:

1. Itch scale is subjective and hence there is no objective way to assess improvement in itching

Sample size calculation

Sample sizes for an α = 0.05 significance level with a two group continuity corrected χ 2 test of equal proportions – 1 sided test, equal sample sizes in each group

Placebo Group	Treatment Reduction	Treatment Group	Sample Size Per Group 80% Power	Sample Size Per Group 90% Power
0.3704	10% Reduction	0.3333	2,102	2,890
0.3922	15% Reduction	0.3333	857	1,174
0.4167	20% Reduction	0.3333	440	599
0.4444	25% Reduction	0.3333	255	346
0.4762	30% Reduction	0.3333	159	214
0.5556	40% Reduction	0.3333	70	90
0.6667	50% Reduction	0.3333	33	43
0.8333	60% Reduction	0.3333	15	19

ITCH SCORE

	1=No		3= Moderate	4= Severe pruritus
	pruritus	(no intervention	pruritus	
		necessary)	(intervention	
			necessary)	
3hrs				
12hrs				

Description of the scores:

- 1. No pruritus- absence of any itching

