- 2. Mild pruritus- presence of itching in only one location of the body (e.g. faces or arm). No intervention necessary as assessed by the investigator and the patient agreeing to the decision. Usually the itching is not relieved by the patient and only reported after being prompted by the investigator/
- 3. Moderate pruritus- presence of itching in more than one location, typical in 2 locations (e.g. arms and thorax). Intervention necessary as assessed by the investigator and the patient.
- 4. Severe pruritus- severe itching which involves almost the entire body and often disturbing the patient.

Score of \geq 3-included in the randomization

Improvement is a score of ≤ 2 at 3hrs

References:

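### Entry itch score (3 or 4) probably predicts 3-hour failure and is already recorded, but the primary comparison does not use it; stratifying by it would be a near-free improvement

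*Combined protocol and SAP*

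**What the plan says.** - **Entry (Study Design):** "Subjects with itch score of ≥ 3 will be randomized in a double blind fashion". On a four-category scale, entry score is therefore 3 or 4. The top category is described as "Severe pruritus- severe itching which involves almost the entire body and often disturbing the patient".
- **Success (Itch Score):** "Improvement is a score of ≤ 2 at 3hrs", with no reference to entry score.
- **Failure:** Study Design says "Treatment failure is defined as an itch score of ≥3 at 3 hours post intervention", which mirrors the success rule. Specific aims says "Treatment failure is defined as persistent itch score of > 3 3hrs after receiving the intervention". The two conflict.
- **Primary Outcome:** "Number of treatment failures in the study group versus the placebo group at 3 hours post randomization".
- **Statistical Method:** "Data will be analyzed using Chi square, student t-tests and Mann-Whitney U test (for non-parametric data) where appropriate". No stratified test, covariate model or stratified randomisation is described.
- **Use of the baseline score:** it determines eligibility and enters secondary outcome 6, "Change in the baseline itch score between treatment and the placebo group". It has no role in the primary comparison.

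**The concern.** A child entering at 3 succeeds by dropping one category. A child entering at 4 must drop two, and a fall from 4 to 3 is a failure. Failure is thus likely to be commoner among those entering at 4. With about 33 children per arm and no stratification, one arm may by chance receive clearly more of them.

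An unadjusted comparison carries that imbalance into the estimated difference. It could flatter cetirizine or hide a real effect, depending on which arm has the excess. A binary covariate already in hand could remove most of this, and the plan does not use it.

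**Working it through.** **1. The plan's own figure.** Inputs from Sample size calculation: failure 0.6667 v 0.3333, one-sided α = 0.05, 80% power, continuity-corrected chi-square.

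- Uncorrected: n = [1.645·√(2·0.5·0.5) + 0.842·√(0.2222 + 0.2222)]² / 0.3333² = (1.163 + 0.561)² / 0.1111 = 26.75.
- Corrected: (26.75/4)·[1 + √(1 + 4/(26.75·0.3333))]² = 32.5, so 33 per arm and 66 in total, as stated.

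**2. Assumptions.** The documents give neither the share q entering at 4 nor failure by entry score. I take q = 15-50% and a failure gap g (failure from 4 minus failure from 3) of 0 to 0.43. Failure is ≥3 at 3 hours, because that mirrors the Itch Score rule; this does not decide which definition should stand. Under > 3 the required falls would be none from 3 and one category from 4, so the asymmetry would remain.

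**3. How often the arms differ.** The SD of the between-arm difference in share is √(2q(1−q)/33). A gap of 20 points or more means at least 7 children (7/33 = 21 points).

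| q | SD (points) | Chance of a gap ≥20 points, either direction |
|---|---|---|
| 15% | 8.8 | about 2% |
| 30% | 11.3 | about 8% |
| 50% | 12.3 | about 11% |

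A gap in one given direction has half that chance.

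**4. Shift in the failure difference.** Shift = imbalance × g. For 20 v 13 children: 0.212 × 0.29 = 0.06 and 0.212 × 0.43 = 0.09, against a planned difference of 0.333.

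**5. Conditional behaviour with no drug effect** (simulation, 33 per arm, 20 v 13 split, one-sided 5%, g = 0.29 and 0.43):

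| Test | Excess of 4s on placebo (favours cetirizine) | Excess of 4s on cetirizine (favours placebo) |
|---|---|---|
| Chi-square, uncorrected | 0.12 and 0.17 | about 0.01 or below |
| CMH by entry score | 0.05 | 0.05 |

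With the continuity correction used for sizing, the first cell becomes 0.08 and 0.11 at a common failure rate of 0.5, or 0.07 and 0.10 at a rate near the planned placebo rate (0.665).

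**6. Conditional behaviour with a drug effect.** Assumed failure from 3/4: placebo 0.52/0.81 and cetirizine 0.18/0.48, or placebo 0.45/0.88 and cetirizine 0.15/0.52. If cetirizine has 20 children entering at 4 and placebo 13, uncorrected chi-square power is 0.75 or 0.67, against 0.89 or 0.91 with CMH.

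**7. Overall behaviour, all randomisations.** With no drug effect, the uncorrected chi-square rejects about 0.05 whatever the gap. With the planned effect, its mean estimated difference stays at 0.333. Power at 0.667 v 0.333, one-sided 5%, no continuity correction:

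| g | Chi-square | CMH |
|---|---|---|
| 0-0.1 | 0.88 | 0.87 |
| 0.2 | 0.88 | 0.87-0.88 |
| 0.3 | 0.88 | 0.88-0.90 |
| 0.4 (q = 30-50%) | 0.88 | 0.91-0.92 |

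At two-sided 5% (q = 30-50%) the chi-square has 0.82, and CMH has 0.78 (g = 0), 0.80 (g = 0.2) and 0.85-0.86 (g = 0.4). The chi-square's two-sided type I error is slightly high here (about 0.054, against 0.05 for CMH), which explains part of the deficit at small g.

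**The case against.** The strongest reply is that nothing here is wrong. An unadjusted chi-square in a 1:1 randomised trial is valid, and prognostic stratification is optional. This stands. A reader might infer that the primary result is biased or the false-positive rate inflated. The documents do not support that: the raised rejection in one direction of imbalance is offset by the lowered rejection in the other, and the overall rate stays near 5%.

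A reader might also infer that the endpoint is defective because some children need two steps and others one. That does not follow either. The scale labels 2 as needing no intervention and 3 as needing one, so a child who falls from 4 to 3 has not reached the success state. Steps on an ordinal scale need not be equal, and how strongly entry score predicts failure is an empirical matter on which the documents give no data.

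Third, the gain is conditional. With a gap of about 0.2 or less, stratifying gains nothing or costs a little power. This stands and belongs with the recommendation.

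Secondary outcome 6 does use the baseline score and would capture a fall from 4 to 3, but it does not adjust the primary comparison. The phrase allowing tests where appropriate does not supply adjustment: only unadjusted tests are listed, and a choice made after seeing the data would be open to challenge.

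**Conclusion.** The point holds as a recommended improvement to the primary analysis. Entry score is a likely predictor of failure, is binary and is already recorded, and nothing in the plan uses it in the primary comparison.

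Stratification mainly protects the one trial that will be run against an unlucky split, in either direction. A split of 20 points or more is uncommon: about 8-11% of trials if 30-50% enter at 4, and about 2% if 15% do. When it happens and the gap is 29-43 points, the estimate moves by 6-9 points. A precision gain is likely only if the gap is about 0.3 or more. All these sizes rest on assumed shares and gaps, and the shift is zero if entry score does not predict failure.

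**What to change.** First reconcile the failure definitions in Specific aims (> 3) and Study Design (≥3), since the stratified analysis cannot be finalised until one is chosen.

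Then add to Statistical Method, before unblinding: the primary comparison of 3-hour failures is a Cochran-Mantel-Haenszel test stratified by baseline itch score (3 v 4), reported with the stratified difference in failure rate and with failures by arm within each entry score. State the sidedness and whether a continuity correction applies; the sizing is one-sided and corrected, and Statistical Method is silent on both.

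The cost is a sentence or two. No new data are needed, and the success cut and randomisation can stay as they are. The downside is a power loss of about 0.01 one-sided (about 0.04 two-sided, 0.82 to 0.78) if entry score turns out not to predict failure.
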